### **13.3. Safety Analysis**

All safety analyses will be performed using the safety cohort of subjects, namely those subjects receiving at least one dose of the study medication.

The following variables will be compared between the treatments for safety purposes:

- Adverse events and serious adverse events
- Laboratory safety variables (Screening to Final Visit)
- Physical examination (Screening to Final Visit)
- Vital signs
- Body weight (Screening to Final Visit)

- ECG (Screening to Final Visit)
- Local tolerability, including:
  - Subjective injection site discomfort as reported by subjects using a 100-mm VAS and ordinal pain scales ([Appendix 2](#)).
  - Erythema and or edema formation at site of injection assessed using the Draize scale ([Appendix 3](#))

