## **9. STUDY TREATMENTS**

### **9.1. Allocation to Treatment**

Subjects will be randomized to one of the 2 treatment groups to receive the appropriate sequence of blinded study medication (see [Table 3](#)). Approximately 80 patients will be randomized with a goal of completing 75 patients, or roughly 37-38 patients per group. If there are a large number of subjects who are randomized but fail to receive either study drug, compensatory enrollment will be utilized to achieve at least 75 evaluable subjects. Each subject will receive a single subcutaneous injection on each of the two (2) treatment days, with a period of 7-28 days between doses.

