  - d. Every 5±2 minutes after glucagon is administered until all symptoms have abated (i.e., all symptoms have score = 1) or 45 minutes post-dosing, whichever occurs first.
9. Local tolerability will be assessed as follows:
  - a. Subjects will complete a Visual Analog (VAS) questionnaire regarding injection site discomfort ([Appendix 2](#)) at 10±5 and 30±5 minutes post-dosing, and again at 240±5 minutes post-dosing if VAS score reported at 30 minutes is > 0 mm.
  - b. Subjects will complete an Injection Site Discomfort Description and Duration Questionnaire at 10±5 minutes post-dosing. If discomfort is ongoing at 10 minutes post-dosing, the questionnaire will be updated before the subject leaves the clinic to document the final duration.
  - c. An investigator will use the modified Draize scales ([Appendix 3](#)) to assess erythema and edema formation at the injection site at 10±5 and 30±5 minutes following administration. Any injection site with a score > 0 for either erythema or edema at 30 minutes post-dosing will be re-evaluated for both at 240±5 minutes post-dosing. If any scores remain > 1 at the 240-minute evaluation, the subject may leave the clinic but will be instructed to contact study staff if the condition fails to resolve.
10. Adverse events reported by the subject or observed by an investigator will be recorded in the CRF.

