### **10.3. Subject Withdrawal**

Subjects may withdraw from the study at any time at their own request, or they may be withdrawn at any time at the discretion of the investigator or Sponsor for safety, behavioral or administrative reasons. If a subject does not return for a scheduled visit, every effort should be made to contact the subject to determine the reason(s) why the subject failed to return for the scheduled visit, and to reschedule the missed visit. This includes contacting subjects via email and telephone, including family members or emergency contacts. If such efforts fail, a certified letter should be sent to the subject’s last known address requesting they contact study staff.

In all circumstances, every effort should be made to document subject outcome. Information regarding the reason for not completing the study will be recorded in the CRF. The investigator should inquire about the reason for withdrawal, request that the subject return for a final visit, and follow-up with the subject regarding any unresolved AEs. It will be documented whether or not each subject completed the study. Any subject who receives at least one treatment dose of study medication will be included in the safety analysis.

If a decision by the investigator or sponsor is made to withdraw a subject, a final visit should be scheduled soon after the decision to withdraw is made. The subject will be asked to return to site for the assessments listed in Section [10.2.3](#).

If the subject withdraws from the study and also withdraws consent, no further evaluations should be performed, and no additional data should be collected. The Sponsor may retain and continue to use any data collected before such withdrawal of consent.

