### 12.2. Reporting Adverse Events

All observed or volunteered AEs regardless of treatment group or suspected causal relationship to the study treatment will be reported with two exceptions. Since it is being experimentally induced in this study, hypoglycemia will not be considered an AE in this study unless the event meets one of the definitions of an SAE (see Section 12.4). Injection site reactions will not be considered an AE unless a skin reaction or pain requires medical intervention.

For all AEs, the investigator must pursue and attempt to obtain information adequate to determine the outcome of the AE and to assess whether it meets the FDA criteria for classification as an SAE, requiring immediate notification to Xeris Pharmaceuticals. For all

AEs, follow-up by the investigator is required until the event resolves or stabilizes at a level acceptable to the investigator to consider it closed. For an unresolved AEs to be considered stable, the Medical Monitor must concur with that assessment.

As part of ongoing safety reviews conducted by the Sponsor, any non-serious adverse event that is determined to be serious (according to the FDA definitions of an SAE) will be reported by the Sponsor as an SAE. To assist in the determination of case seriousness, further information may be requested from the investigator to provide clarity and understanding of the event in the context of the clinical study.

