### **12.3. Reporting Period**

For all AEs, the reporting period to Xeris Pharmaceuticals begins from the subject providing informed consent, through the Follow-up Visit. All adverse events will be followed until resolution or the subject is medically stable.

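### Adverse events during insulin induction appear in no planned safety summary if the subject is never dosed, and in dosed subjects they are not separated from events after the dose

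*Combined protocol and SAP*

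**What the plan says.** **Who is analysed.** Section 13.3 bases every safety analysis, without exception, on the safety cohort, "namely those subjects receiving at least one dose of the study medication". Section 10.3 repeats the rule: "Any subject who receives at least one treatment dose of study medication will be included in the safety analysis". Section 13.3.1 summarizes AEs by system organ class and study drug and counts exposed subjects.

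**What is collected.** Section 12.3: "For all AEs, the reporting period to Xeris Pharmaceuticals begins from the subject providing informed consent, through the Follow-up Visit". Section 10.2.1, step 10, has no post-dose limit: "Adverse events reported by the subject or observed by an investigator will be recorded in the CRF". Section 12.2 makes one relevant exception: "hypoglycemia will not be considered an AE in this study unless the event meets one of the definitions of an SAE". Section 12.4 gives convulsions not leading to hospitalization as an example of a serious event.

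**Order of events.** In Section 10.2.1, randomization is step 6 and induction starts at step 7. Study drug follows only after two consecutive glucose readings below 50.0 mg/dL. If these are not reached within 3 hours, study drug is withheld and the visit is rescheduled.

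**Subjects who get neither drug.** Section 9.1 contemplates subjects who are "randomized but fail to receive either study drug", and provides compensatory enrollment if there are many. Section 13.1 removes such subjects from the ITT cohort as well.

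**The concern.** Insulin induction is a study procedure with its own risk, and every subject must pass through it before receiving glucagon. The collection window covers that interval, but the analysis population does not cover everyone exposed to it. A subject who has an adverse event during a first induction and never receives study drug belongs to neither the safety cohort nor the ITT cohort.

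There is a second, smaller gap among dosed subjects. An event that starts during induction cannot be due to the glucagon given later at that visit. Section 13.3.1 nevertheless tabulates AEs by study drug with no rule for such events.

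At stake are the completeness of the aggregate record of procedure harm and the cleanness of the by-drug AE counts. The study report could not fully check, from its planned summaries, the expectation in the Synopsis that induction will not impair consciousness.

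**Working it through.** The plan states no figure on this point, so there is nothing to reproduce. The check sets the sections side by side.

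1. **Is there a pre-dose interval in which harm can occur?** Yes. Sections 7.2 and 10.2.1 place insulin bolus and infusion between randomization and dosing, with up to 3 hours to reach the glucose target.
2. **Are events in that interval collected?** Yes, under Section 12.3 and Section 10.2.1, step 10. Induced hypoglycemia itself counts only if it meets an SAE definition (Section 12.2).
3. **Is any analysis set open to a never-dosed subject?** No. Section 13.3 requires a dose, Section 13.1 drops subjects who received neither drug, and Section 13.3.1 counts exposed subjects. No enrolled, randomized or induction-exposed safety set is described.
4. **Where does an induction event go?**

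| Event during induction | Recorded | In safety cohort | Place in by-drug table |
|---|---|---|---|
| First treatment visit, subject never dosed | yes | no | none |
| First treatment visit, subject dosed then or at a rescheduled visit | yes | yes | not specified |
| Second treatment visit, subject dosed at the first | yes | yes | not specified |

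In the third row, the event meets the Section 12.1 definition of treatment-emergent, because it starts after study treatment began. Section 13.3.1 does not use that definition, and it would not separate induction events at the second visit if it did.

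5. **Scale, by assumption only.** Section 9.1 gives about 80 randomized. Suppose all 80 start induction, k are harmed at the first induction and never dosed, and the rest are dosed.

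- A summary of all induced subjects shows k/80, and the safety cohort shows 0/(80 − k) for these events.
- k = 0: 0/80 in both.
- k = 1: 1/80 = 1.25% against 0/79.
- k = 5: 5/80 = 6.25% against 0/75.

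For an assumed per-subject probability p of such harm, the chance of at least one case is 1 − (1 − p)^80 and the expected number is 80p:

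| Assumed p | Chance of at least one | Expected number |
|---|---|---|
| 0.5% | 33% | 0.4 |
| 1% | 55% | 0.8 |
| 2% | 80% | 1.6 |
| 5% | 98% | 4.0 |

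The documents support none of these rates. The figures show only how the omission would look if such cases occurred.

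**The case against.** The strongest reply is that the cohort fits the objective. Section 5.2 asks for a comparison of the safety of two glucagon products, and no objective or endpoint is to estimate induction harm. An event before any glucagon cannot be attributed to either product. Randomization precedes induction and both subject and investigator are blinded, so nothing suggests that the exclusion favours one drug. All of this stands, and it is why the dosed cohort should stay for the comparison.

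Three stronger readings are tempting, and the documents do not support them.

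- *The events vanish from safety oversight.* They do not. They are entered in the CRF. If serious, they go to the sponsor within 24 hours of awareness (Section 12.9), and to the IRB and, where expedited criteria are met, to FDA (Section 12.11). They are absent only from the aggregate summaries.
- *The worse the event, the more surely it is dropped.* This is inference. The one explicit rule for an induced subject who is not dosed concerns failure to reach the glucose target. That visit is rescheduled, so the subject may still enter the cohort. Section 9.1 is conditional and gives no reason for non-dosing.
- *About half of all dosing-preventing events would be lost*, because first and second inductions are roughly equal in number. That would be a share of an unknown and possibly zero count, under an untested assumption of equal risk at both visits.

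Section 13.5 also defers detail to a SAP, and the text in hand contains no separate one. A listing for never-dosed subjects could be there. The wording of Section 13.3 is unqualified, however, so the protocol text should be brought into line with it.

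**Conclusion.** The point holds at low severity. By its stated rules, the plan collects AEs during induction but has no planned summary for those in never-dosed subjects. It also does not say how induction-phase AEs in dosed subjects are handled in the by-drug tables. A reader might infer that the tables will mix pre-dose and post-dose events. The text leaves this unspecified and does not show that it will happen.

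The primary non-inferiority result is unaffected, and nothing indicates bias in the drug comparison. The size cannot be given because the documents state no induction-harm rate. The conclusion rests on the order of procedures in Section 10.2.1, the population rule in Section 13.3, and the absence of any other safety set or listing in the available text.

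**What to change.** In Section 13.3 and in the SAP:

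1. Keep the dosed cohort for the between-drug comparison.
2. Count in the by-drug AE tables only events with onset after study drug administration. State that an event beginning between first insulin at a visit and that visit's dose is assigned to induction and to neither drug. This matters at the second treatment visit, where such an event also falls after the first drug.
3. Add one descriptive table or listing for all subjects in whom induction was started. Show AEs and SAEs with onset from first insulin to dosing or visit termination, by visit, and flag never-dosed subjects.

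The data are already collected and no clinical rule changes. The cost is one extra table or listing, and reported event counts may be slightly higher.

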#### **13.3.1. Adverse events:**

All AEs will be coded by the Medical Monitor using the Medical Dictionary for Regulatory Activities (MedDRA) and summarized by system organ class and study drug. A summary table indicating the number and the percentage of exposed subjects having at least one AE will be made.

#### **13.3.2. Laboratory safety assessments:**

Laboratory values (biochemistry and hematology) will be flagged if outside the normal range. A listing of abnormal values will be presented in an end of text (EOT) listing. The individual values will be listed indicating values outside normal range. Laboratory assessments will be summarized at Screening and at end of trial.

#### **13.3.3. Physical examination:**

Subjects with any findings in the physical examination evaluation at Screening will be listed. Changes to physical examination from Screening to end of trial will be recorded as AEs if the Investigator judges these as being clinically significant.

#### **13.3.4. Vital signs and body weight:**

Vital signs will be summarized by descriptive statistics.

#### **13.3.5. ECG:**

Any deviation from normal ranges of the measured laboratory parameters will be documented and followed as appropriate. The Investigator's evaluations will be summarized in an EOT listing.

Clinically significant deviations/changes from the Screening Visit to the Final Visit will be documented as AEs if the Investigator judges these as being clinically significant.

#### **13.3.6. Local Tolerability:**

The incidence of any injection site discomfort (score >0 on the ordinal rating scale) will be analyzed descriptively. The incidences of erythema and edema will be analyzed in a similar manner. Descriptive statistics (only) will be provided for time of onset and duration (of discomfort) and discomfort description (i.e., pain, irritation, itching, etc.). Mean VAS scores will be compared between the treatments.

#### **13.4. Subgroup Analysis**

Safety and efficacy by gender (male, female), age (18-64 years, 65 years and above), and race (non-Hispanic Whites, Hispanics, and African-Americans) will be analyzed descriptively.

#### **13.5. Interim Analysis**

If the total number of subjects with criterion failures (counted in a blinded fashion) exceeds 4, a monitoring statistician not otherwise involved with study conduct may provide an unblinded determination the distribution by treatment group for futility, and communicate a finding of futility to Xeris' upper management for further decisions, while the study team remains blinded. Success will not be tested and no penalty for this futility only check is planned.

More specific details regarding the analyses outlined in 13.1-13.5 will be provided in the Statistical Analysis Plan (SAP) for this protocol.

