#### 13.1.1. Primary Endpoint:

The G-pen acceptance criterion will be based on the sample mean of the treatment minus control failure scores from each subject in the ITT population. If  $D_{ht}$  is the sample mean of the G-Pen minus control failure difference, and SE is the estimated standard error of  $D_{ht}$  (square root of the estimated G-Pen minus control variance divided by the sample size), then the G-Pen will be accepted provided:

$$D_{ht} + 2.6 SE \leq 0.1.$$

This criterion, particularly the value 2.6, came from Monte-Carlo simulations from selected scenarios where the population G-Pen failure rate exceeded the control rate by 0.1. Under these circumstances the rate of G-Pen acceptance was found to be within 0.025 using this criterion, with missing data rates within 15%. This bound of 0.025 on the type 1 error rate was observed for control failure rates up to 5%. Monte Carlo simulation rather than asymptotic normality is necessary because an observed failure from either G-Pen or control is expected to be low, less than 5%.

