#### 13.1.2. Sample Size Calculation:

Using the above criterion, a sample size of 75 subjects yields probabilities of G-Pen acceptance of over 90% if the population failure rates of G-Pen and control are equal, and the rate of missing observations is within 15%. These results were obtained using Monte Carlo simulations with G-Pen and control total failure rates up to 5%, and with G-Pen success Control failure, or G-Pen failure Control success within 1%.

The power and type 1 error bounds were obtained from a simulation model using a 3x3 table of outcomes for G-Pen and control. The three outcomes for each were Success, Failure, and Missing. Probabilities were assigned to each of the 9 cells, with the missing outcome being

stochastically independent of the Success, Failure outcome combinations. Also the failure score difference, G-Pen minus control, was assigned to each of the nine cells. To simulate one replicate of the study, 75 independent draws were made from the multinomial distribution determined by the probabilities from the 9 cells, and the sample mean, estimated standard error were computed. The G-pen acceptance criterion was applied and either a 0 (G-pen failed) or 1 (G-pen accepted) was recorded. This was repeated 10,000 times to obtain the estimated probability of G-pen acceptance under the conditions defined by the cell probabilities. The simulations were performed using R version 3.1.2 (2014-10-31).

Approximately 80 subjects will be randomized at approximately 8 clinical sites with a goal of no single center accounting for > 20% of the total randomization.

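### The futility look is triggered by failures that cancel out of the primary statistic and has no stated boundary; the only printed count rule would not deliver the stated power.

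*Combined protocol and SAP*

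**What the plan says.** Section 13.1.1 bases acceptance on the mean, over ITT subjects, of the G-Pen failure score minus the control failure score. G-Pen is accepted if Dht + 2.6 SE ≤ 0.1.

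Section 13.1.2 states that "a sample size of 75 subjects yields probabilities of G-Pen acceptance of over 90"% when the true failure rates are equal. The range covered is "G-Pen and control total failure rates up to 5"%, with "G-Pen success Control failure, or G-Pen failure Control success within 1"%, provided "the rate of missing observations is within 15"%. The simulation is described as follows: "75 independent draws were made from the multinomial distribution determined by the probabilities from the 9 cells", after which the acceptance rule is applied once. No futility step is mentioned.

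Section 13.5, repeated in the Synopsis, gives the trigger: "If the total number of subjects with criterion failures (counted in a blinded fashion) exceeds 4". A monitoring statistician outside study conduct is then permitted, not required, to examine the split by treatment and to report futility to upper management. The study team stays blinded. Success is not tested and no penalty is planned. No futility boundary is given, and further detail is deferred to a SAP.

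Just before its futility paragraph, the Synopsis also prints a second acceptance rule, applied after the 75th evaluable subject completes both periods: G-Pen failures not above 4, and G-Pen minus control failures not above 3. Section 13.1.1 does not contain this rule.

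**The concern.** The trigger and the primary statistic measure different things. A subject who fails at both visits scores 1 − 1 = 0, so says nothing against non-inferiority under section 13.1.1, yet counts in full toward the trigger. If most failures are of this kind, the look can open in trials where G-Pen is doing as well as control.

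That would matter little if the look were judged by section 13.1.1, but the plan does not say so. The only count benchmark on paper is the Synopsis rule, whose G-Pen limit of 4 matches the trigger threshold and also counts failures on both drugs. A futility-only check needs no alpha adjustment, but it can cost power, and the stated power includes no such cost.

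**Working it through.** **Inputs.** n = 75; failure rate per drug p up to 5%; discordance up to 1% each way; missing up to 15% (all section 13.1.2). Missing scores are 0.2 for G-Pen and 0.1 for control (section 13.1). The acceptance rule is from section 13.1.1, the trigger from section 13.5, and the count rule from the Synopsis. Assumption: a criterion failure means plasma glucose not above 70.0 mg/dL within 30 minutes.

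**Step 1: the plan's own figure.** Cells at the ceiling: both fail 4%, G-Pen only 1%, control only 1%, both succeed 94%. Simulated acceptance under section 13.1.1 is 99.3% with complete data and 90.7% with 15% missing independently per drug. The stated power over 90% is reproduced.

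**Step 2: the trigger.** With 1% discordance each way, P(subject has any failure) = (p − 0.01) + 0.01 + 0.01 = p + 0.01. The look may open with probability P(X > 4), X ~ Binomial(75, p + 0.01). The other columns come from multinomial simulation (1,000,000 replicates, complete data, equal drugs).

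| p per drug | Any failure | Look may open | Triggered trials meeting 13.1.1 | Accepted, 13.1.1 | Accepted, Synopsis count rule |
|---|---|---|---|---|---|
| 1% | 2% | 1.7% | 77% | 99.3% | 99.6% |
| 2% | 3% | 7.5% | 93% | 99.3% | 98.1% |
| 3% | 4% | 18.1% | 97% | 99.3% | 92.5% |
| 4% | 5% | 32.1% | 98% | 99.3% | 81.8% |
| 5% | 6% | 47.1% | 98.6% | 99.3% | 67.9% |

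At the ceiling, 4 of every 6 failing subjects fail on both drugs. The count-rule column is almost entirely the limit on G-Pen failures: P(X > 4), X ~ Binomial(75, 0.05) = 32.1%, and 1 − 0.321 = 0.679.

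**Step 3: missing data at the ceiling.** With 15% missing independently per drug, P(any observed failure) = 0.04 × (1 − 0.15²) + 0.02 × 0.85 = 0.0391 + 0.0170 = 0.0561. The look may open in 41% of trials, and 83% of those would be accepted under section 13.1.1.

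**Step 4: the power cost depends on the boundary.** At the ceiling with complete data:
- Judged by section 13.1.1: close to no loss from 99.3%.
- Judged by the count rule: 99.3 − 67.9 = 31.4 points lost.
- Every triggered trial stopped: acceptance about 53%, a loss of about 46 points.

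**Step 5: what a trigger tied to section 13.1.1 needs.** With g G-Pen-only and c control-only failures, n = 75 and complete data, Dht = (g − c)/75 and SE = √{[(g + c) − 75·Dht²]/(74 × 75)}.
- g = 3, c = 0: 0.0400 + 2.6 × 0.02278 = 0.0992, accepted.
- g = 4, c = 0: 0.0533 + 2.6 × 0.02612 = 0.121, not accepted.
- g = 4, c = 1: 0.0400 + 2.6 × 0.02965 = 0.117, not accepted.
- g = 4, c = 4: 0 + 2.6 × 0.03797 = 0.0987, accepted.

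So 4 discordant subjects can already breach the criterion. The last two lines show that all remaining outcomes being successes is not the best case for G-Pen, because later control-only failures can bring a trial back inside the margin.

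A trigger at 4 or more discordant subjects opens with probability P(X ≥ 4), X ~ Binomial(75, 0.02) = 6.4%, whatever the failure rate on both drugs.

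**The case against.** The strongest reply is that the trigger only permits a look. One uninvolved statistician may be unblinded, the study team is not, and the Synopsis allows the answer that the trial continues. That stands: opening the look stops nothing and costs no power.

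The 47% is also the top corner of a range. Section 13.1.1 expects failures below 5%, and at 1% to 3% the look opens in 1.7% to 18% of trials. That stands too. A reader might infer that nearly half of all trials of an equally effective G-Pen will be unblinded, or that about a third will be declared futile. The documents support neither. The first takes the ceiling as the expected case. The second assumes that the statistician applies the Synopsis count rule, which section 13.5 does not say.

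Failures on both drugs are not irrelevant everywhere: they count toward the Synopsis limit of 4 G-Pen failures, and with 4 or fewer failing subjects that limit cannot be breached. The trigger therefore fits the Synopsis rule. This explains the threshold but exposes the conflict, since the two rules accept 67.9% and 99.3% of the same trials.

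Finally, the deferred SAP might set a boundary. The document in hand contains no such text, and the trigger and the count rule are fixed in the protocol as it stands.

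A discordance trigger is no cure-all. If failures on the two drugs were independent at 5%, discordance would be 2 × 0.05 × 0.95 = 9.5%, and the look would open in 93% of equal-drug trials at 4 or more discordant subjects, against 87% with the present trigger. That case lies well outside the 1% discordance used for sizing.

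**Conclusion.** The point holds in limited form. The trigger counts subjects who are neutral under section 13.1.1, no futility boundary is stated, and the one printed count benchmark conflicts with the primary criterion. Within the plan's own range, the look may open in 1.7% to 47% of equal-drug trials with complete data. At the ceiling nearly all of those would go on to meet section 13.1.1.

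The power cost is undefined rather than demonstrated: near zero if section 13.1.1 guides the decision, about 31 points at the ceiling if the count rule does. At 4% and 5% failure the count rule, used as written, does not reach the stated power.

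These figures assume equal true failure rates, 1% discordance each way, 75 subjects and, except where stated, complete data. Lower failure rates shrink the problem quickly.

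**What to change.** In section 13.5 and the Synopsis:

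1. Reconcile the Synopsis count rule with section 13.1.1 so that one acceptance criterion applies, and state that futility is not judged by the count rule.
2. Trigger the look on 4 or more subjects with discordant outcomes across their two visits. In a crossover this can be counted without treatment codes. State how a failure paired with a missing outcome is counted; a G-Pen failure with control missing scores 1 − 0.1 = 0.9.
3. Call futility only when Dht + 2.6 SE ≤ 0.1 cannot be met under any possible remaining outcomes. No trial that could still be accepted is then stopped, and the printed power is unaffected. If a less strict boundary is preferred, state it and restate the power with it included.

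The cost is a few sentences, plus a rerun of the simulation only if a less strict boundary is chosen. There are two small downsides: a first-visit failure is not counted until the second visit is done, and the strict boundary will seldom stop a trial early.
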